#### **4. Stopping Rules**

1. Accrual of less than 12 patients in the first year

#### **5. Subject Selection**

##### **5.1 Inclusion criteria**

1. Prior first allogeneic stem cell transplant, with any graft source, donor type, and GVHD prophylaxis.
2. Patients who are on one systemic immunosuppressive agent for chronic GVHD with a plan to withdraw all systemic IST. Hydrocortisone or prednisone continued for treatment of adrenal insufficiency are not considered a systemic IST.
3. No evidence of malignancy at the time of enrollment.
4. Agree to be evaluated at the transplant center or by local provider every 3 months for 12 months after randomization.
5. Agreement to be contacted by phone or e-mail for health status evaluation for up to 3 years.
6. Signed, informed consent

##### **5.2 Exclusion criteria**

1. Inability to comply with study procedures
2. Pregnancy

#### **6. Study Procedures**

##### **6.1 Study Design**

We plan to enroll 40 patients in 2 years. Patients are eligible for enrollment at any time after an allogeneic transplant, as long as they were diagnosed with chronic GVHD, are on one immunosuppression agent, and are planning to withdraw all IST. Patients will be randomized to either IST discontinuation (following standard of care practice) or continuation of IST for an additional 9 months (investigational). If patients are enrolled on the study prior to reaching the IST dose that the attending physician recommends

they continue should they be randomized to the continuation IST arm, randomization will take place before the patient gets to the IST dose that would be continued if they are randomized to the IST continuation arm (investigational arm). If patients are enrolled on the study while they are already taking the IST dose that the attending physician recommends they continue should they be randomized to the continuation IST arm, randomization will take place at time of enrollment (Figure 1). Randomization will occur within three months of study enrollment. Patients will be actively followed for 12 months after randomization. After active participation will continue long term annual follow up via chart review.

Patients on the discontinuation IST arm will have their IST tapered and discontinued per the plan of the treating physician, while patients on the continuation IST arm will continue a fixed dose IST for an additional 9 months with no taper. After 9 months, IST may be tapered.

The dose of IST to be continued, if a patient is randomized to the continuation IST arm, will be determined by the attending physician at the time of enrollment based on the following overarching guidelines in the table below:

Immunosuppressive therapy	Age 18 years	Age <18 years
Cyclosporine	Continuation dose should result in a level < 120 ng/mL	
Tacrolimus	Continuation dose should result in a level < 5 ng/mL	
Sirolimus	Continuation dose should result in a level < 3 ng/mL	
Mycophenolate mofetil	Continuation dose ≤ 500 mg BID	Continuation dose ≤ 7.5 mg/kg BID
Prednisone	< 20 mg/day or < 40 mg every other day	< 0.25 mg/kg/day or < 0.5 mg every other day
Any other agent	Defined by the treating physician at the time of enrollment	

For further evaluation of adult patients' health status, adult participants will be asked to complete a survey (Appendix A) based on the PROMIS-29 and Lee Symptom Scale. Please note that patient surveys might be reformatted for ease of completion and to ensure uniform font and style in the two documents or to correct any formatting or typographical errors. However, no questions will be added without IRB approval.

Patients will be asked to complete the survey at enrollment, randomization, every 3 months after randomization, at the end of the active study participation (12 months after randomization), and if IST resumed/dose increased (if still during the active study participation period).

The Patient-Reported Outcomes Measurement Information System (PROMIS®), is a set of person-centered measures developed with NCI support (10). The PROMIS-29 profile contains 7 PROMIS domains with 4 questions each (short-forms using Likert scales), and one pain intensity (0-10) question. All PROMIS scores use a standardized t-score metric against normative data for the U.S. general population (11, 12). The scale takes less than 5 minutes to complete.

[figure not shown]
The Lee cGVHD symptom scale is a 30 item measure with 7 domains capturing bothersome symptoms from chronic GVHD (13). The Lee cGVHD symptom scale is sensitive to change in patient status with 6-7 point differences being clinically meaningful (14, 15). The scale takes 2-5 minutes to complete.

Pediatric patients will not be asked to complete the surveys, which were designed to the adult population. No Patient-Reported Outcomes Measurement or symptom scale surveys have been validated for transplant pediatric population. Thus, pediatric participants would not be asked to complete surveys.

Whole blood samples will be collected for research. All effort will be made to collect 40 mL blood samples (see table for children  $\leq 40$  kg) at enrollment, randomization, and monthly until one year after randomization, and at times of IST resumption or dose increase.

	25-40 kg	10-24.99 kg	<10 kg
Maximum volume of each blood draw	20 mL	10 mL	5 mL
Maximum volume in 1 year	260 mL	130 mL	65 mL

Patients may participate without donating blood but every effort will be made to collect the samples, including use of remote draw and overnight shipping.

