## 1. Background and Rationale

Patients who received allogeneic hematopoietic cell transplantation (HCT) typically require administration of immunosuppressive treatment (IST) for at least 6 months in order to prevent or treat graft-versus-host disease (GVHD). GVHD is the most serious and common complication of allogeneic HCT. Significant acute GVHD occurs in 20-50% of patients,(1-3) and chronic GVHD occurs in 30-60% of patients who survive more than 100 days after transplantation.(3, 4) Duration of IST is typically prolonged once patients develop GVHD. Particularly, duration of IST in patients who have chronic GVHD is reported to exceed 2-3 years.(5, 6) While IST is important to reduce mortality and morbidity associated with GVHD, it may increase risks of infection, recurrent malignancy and secondary malignancy.(7)

“Immunologic tolerance” may be defined as the absence of immune-mediated injury when immunosuppressive medications are no longer given. Unlike solid organ transplantation,(8) many patients after allogeneic HCT can achieve sufficient “functional” tolerance even after development of GVHD, and can eventually stop all IST permanently without developing active manifestations of GVHD. However, many patients, especially those with chronic GVHD, develop GVHD exacerbation and require resumption of IST. Currently, there are no clinical or biological predictors for successful IST discontinuation, and management of chronic GVHD patients consists of repeated attempts to taper and stop IST.

A recent retrospective evaluation of 250 adult patients who received systemic treatment for chronic GVHD at the Fred Hutchinson Cancer Research Center (FHCRC)/Seattle Cancer Care Alliance (SCCA) demonstrated that although 51% patients were able to stop IST at least one time, 46% of these patients required resumption of IST after a median of 3.4 months off therapy (IQR 2.1-8.0), due to GVHD exacerbation (9). Among patients stopping IST a second time, 30% restarted at a median of 6 months.

Resumption of IST for chronic GVHD exacerbation may increase the morbidity and mortality of patients, since common practice is to reinstitute high doses of IST initially, followed by a taper again to the lowest dose. Additionally, GVHD may fail to be controlled after resumption of IST, or irreversible organ damage may occur each time GVHD symptoms flare.

A potential alternative approach to the current practice of repeated attempts to taper and stop IST is continuation of IST.

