The purpose of this study is to enroll a cohort of patients with chronic GVHD whose treating physician is planning to taper their IST to off, and to randomize them to either discontinuation of IST (standard approach) or continuation of IST for another 9 months (investigational approach), in order to evaluate the effect of prolonged IST on chronic GVHD control, with the hypothesis that this approach would decrease the risk of GVHD exacerbation and decrease the need to resume high doses of IST. The rational for the 9 months extended IST in the continuation IST arm is retrospective data demonstrating

that >75% of patients who resumed IST after discontinuation, restarted within 9 months of IST discontinuation.

The rationale for the feasibility study is that a large sample size is needed to demonstrate statistically significant differences between the two treatment approaches. Thus, prior to proceeding with a large study we need to conduct a feasibility study to evaluate whether patients can be enrolled, randomized, and follow their assigned treatment, and to assess whether the observations about IST resumption in the retrospective study appear accurate. We acknowledge the heterogeneity among the target patient population (e.g. donor and stem cell source, time since transplant, and IST), but despite this heterogeneity when patients are ready to taper IST they are more similar than different in their clinical status. Information from this feasibility study are necessary to help us design a larger study and apply for external funding. In the larger study, we plan to use stratified randomization to help balance underlying patient and transplant characteristics.

Biological samples will be collected during the study to analysis of blood profiles and cellular signatures of “functional” tolerance and biomarkers of GVHD exacerbation.

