### 3.2 Secondary Endpoint

- Successful randomization of patients
- Compliance with treatment and data collection as outlined in the protocol
- Evaluate enrollment rate and quality of data of patients who are not local
- Rate of IST resumption (discontinuation IST arm)/increase IST dose (continuation IST arm) by 12 months after randomization

- New chronic GVHD manifestations and/or worsening of existing manifestations, recurrent malignancy by 12 months after randomization, grade  $\geq 3$  infections, and grade  $\geq 3$  organ toxicity.

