**Figure 1. Study design**

## 6.2 Study Design Rationale

Need for a feasibility study: This study is based on the hypothesis that prolonged low dose IST will prevent GVHD exacerbation and need to resume of high doses of IST. Preliminary data in support of this hypothesis are derived from a retrospective study demonstrating that approximately half of patients with chronic GVHD who stop IST need to restart treatment after a median of 3-6 months. The only way to test this hypothesis is with a randomized trial but the sample size for such a study is prohibitive without evidence that patients can be enrolled and randomized, that they will follow their assigned treatment, and that the observations about IST resumption in the retrospective study appear accurate.

Justification for allowing heterogeneity in last agent, tapering schedules, and dose to continue in the intervention arm: As patients with chronic GVHD respond to a variety of immunosuppressive agents and doses, there is no unified treatment protocol for chronic GVHD. Similarly there are no uniform criteria when attempts to stop IST should be initiated. In our retrospective study the last immunosuppressive regimen to be discontinued was variable, including calcineurin inhibitors (43%), prednisone (28%), sirolimus (19%), or mycophenolate mofetil (10%). Thus, after discussion with the LTFU attendings, we elected to allow heterogeneity in plans for IST taper timing and speed. This study design mirrors routine clinical practice and allows us to capture data about the most common practices regarding IST discontinuation. At the time of enrollment, physicians must specify the dose/schedule at which they are comfortable randomizing a patient to possibly continue stable treatment for an additional 9 months. Ideally, this would be a dose that does not cause toxicity and also controls GVHD.

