Enrollment time: We will enroll patients at the time when they are only taking one immunosuppressive agent, chronic GVHD is under control and the plan is to start tapering IST, or when patients are already tapering IST. Patients may be enrolled on the study before or at the time they are taking the IST dose that the attending physician recommends they continue should they be randomized to the continuation IST arm. Enrolling patients before or at the time they reach the IST dose that may be continued should they be randomized to the continuation IST arm (Figure 1) allows us to present the protocol to patients when they are seen in the clinic, which will increase the chance of enrolling patients on the study (Patients with well controlled GVHD are seen in clinic infrequently and thus may be seen before or at the time they have already reached the lower IST dose to be continued).

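### The check on the retrospective IST-resumption figures uses a clock that starts at randomization, whereas those figures run from IST stop; the remaining taper, which has no stated limit, biases the observed rate downwards.

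*Combined protocol and SAP*

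**What the plan says.** Section 6.2 of the combined protocol and SAP justifies the study partly by the need for evidence that "the observations about IST resumption in the retrospective study appear accurate"; section 1 gives the same reason. The observations in question, in section 1, start when treatment stops. Among patients who stopped at least once, "46% of these patients required resumption of IST after a median of 3.4 months off therapy (IQR 2.1-8.0"). More than 75% of "patients who resumed IST after discontinuation, restarted within 9 months of IST discontinuation".

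The trial's rate, in section 3.2, runs on a different clock: "Rate of IST resumption (discontinuation IST arm)/increase IST dose (continuation IST arm) by 12 months after randomization".

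Patients are on IST when that clock starts. Section 6.2 enrolls them when "the plan is to start tapering IST, or when patients are already tapering IST". Under section 6.1 they are randomized on enrollment if already at the continuation dose; otherwise "randomization will take place before the patient gets to the IST dose that would be continued". After that, "Patients on the discontinuation IST arm will have their IST tapered and discontinued per the plan of the treating physician". The one time limit nearby is "Randomization will occur within three months of study enrollment", which covers the interval before randomization and not the taper after it. The table in section 6.1 caps the continuation dose, not the length of the taper. Section 6.2 leaves taper timing and speed open on purpose.

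The monthly contact in section 6.5 asks whether IST was restarted; a stop date is not listed. Sections 7.1.2 and 7.1.3 specify no analysis timed from IST stop.

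**The concern.** A patient who is still tapering has not stopped and so cannot restart. In the discontinuation arm the 12 months after randomization therefore divide into remaining taper and time off IST, and only the second part is comparable with the retrospective data. The longer the tapers, the fewer restarts fall inside the window, even if the risk after stopping is exactly as the retrospective study found.

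A low observed rate would then have two explanations that the planned summary cannot separate: fewer flares than expected, or slow tapers. Section 1 says that information from this study will be used to design the larger trial, so a low figure taken at face value could carry into that trial's control-arm assumption.

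**Working it through.** **The plan's own figure.** Section 7.2 states 83% power for 75% versus 30% with 20 per arm at two-sided 0.10. Full enumeration of the two-sided Fisher test gives 82.3%, so that figure reproduces. Nothing below depends on it.

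**Inputs**
- Share who resume after stopping: 0.46 (section 1).
- Timing among resumers, in months off IST: F(2.1) = 0.25, F(3.4) = 0.50, F(8.0) = 0.75 (section 1). As a check, F(9) should exceed 0.75 (section 1).
- Window: 12 months from randomization (section 3.2).
- Patients in the arm: 20 (section 7.2).
- Month *s* after randomization at which IST stops: not in the documents. Assumed values are 0, 3, 4 and 6, the same for all 20 patients.

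**Formula.** Months off IST by month 12 = 12 − s, so the expected observed rate = 0.46 × F(12 − s).

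**One point needs no curve.** With s = 4, 8.0 months are left. F(8.0) = 0.75, so 0.46 × 0.75 = 34.5%, or 6.9 of 20.

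**Other points need a curve through the quartiles.** Four were used:
- Linear between quartiles, with an assumed upper end of 24 months. F(12) = 0.75 + 0.25 × 4/16 = 0.8125; F(9) = 0.75 + 0.25 × 1/16 = 0.766; F(6) = 0.50 + 0.25 × 2.6/4.6 = 0.641.
- Lognormal A: median 3.4, sigma = ln(8.0/2.1)/(2 × 0.6745) = 0.99.
- Lognormal B: mu 1.35, sigma 0.99, fitted to all three quartiles.
- Weibull: shape 1.19, scale 5.5, fitted to all three quartiles.

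| Curve | s = 0 | s = 3 | s = 4 | s = 6 | Loss, 0 to 3 | Loss, 0 to 6 |
|---|---|---|---|---|---|---|
| Linear | 37.4% | 35.2% | 34.5% | 29.5% | 2.2 | 7.9 |
| Lognormal A | 41.3% | 38.5% | 37.1% | 33.0% | 2.8 | 8.3 |
| Lognormal B | 40.2% | 37.0% | 35.4% | 30.9% | 3.2 | 9.3 |
| Weibull | 42.3% | 38.4% | 36.4% | 30.8% | 3.9 | 11.5 |

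In patients, the loss is 0.4-0.8 of 20 for a stop at month 3 (20 × 0.022 to 20 × 0.039) and 1.6-2.3 of 20 at month 6 (20 × 0.079 to 20 × 0.115).

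**Quality of the curves.** No smooth curve meets all three quartiles. At 3.4 months, where F should be 0.50, Lognormal B gives 0.449 and the Weibull 0.431. At 8.0 months, where it should be 0.75, Lognormal A gives 0.806 and the Weibull 0.790. All four exceed 0.75 at 9 months. The spread across rows is a fair picture of this uncertainty.

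**What is not due to the taper.** Even with s = 0 the rate is below 46%, because on every curve some resumers restart after 12 months. The taper effect is the loss from s = 0, not the distance from 46%.

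**Sampling error.** Exact 95% intervals are 19-64% for 8 of 20 and 12-54% for 6 of 20, much wider than any loss in the table.

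**The case against.** The strongest reply is that the design is deliberate and little depends on this rate. Section 6.2 argues for free tapers because there is no unified chronic GVHD regimen, and randomization is the right starting point for comparing arms. Checking the retrospective data is a plausibility aim, not an endpoint or decision rule; secondary analyses are descriptive; and sampling error exceeds the bias. All of this stands, and it limits the weight of the point. It does not remove the mismatch: sampling error has no fixed direction, whereas lost time off IST can only lower a rate of restarts.

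That direction depends on how resumption is read. Section 3.2 pairs resumption with the discontinuation arm and dose increase with the continuation arm, which favours restarting after a stop. But section 6.4 collects data at resumption or dose increase without separating arms. If dose increases during the taper counted as events in the discontinuation arm, the direction would no longer be certain.

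Much is also recoverable. Provider assessments, patient records and annual chart review of IST status would probably yield stop dates and later restarts. That makes the fix easy, but no such analysis is planned.

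Two stronger readings are tempting. A reader might infer that clinicians could slow tapers once they know the allocation, undetected because no planned stop date is fixed beforehand. The documents do not show that this would happen. The provider survey completed after consent (section 6.5) is not reproduced and may hold the plan, and Figure 1 is not shown. The actual stop date is in any case enough to check the retrospective rate. A reader might also infer that the 83% power in section 7.2 is overstated because 75% is a from-stop rate. Section 7.2 words it as the arm's 12-month rate, and the matching endpoint runs from randomization, so the text does not support that reading.

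**Conclusion.** The point holds as a limited one. The plan gives no rate on the same clock as the retrospective observations it sets out to check, and the rate it does give is biased low by an amount set by taper length. With the retrospective 46% and its timing, the taper costs about 2-4 percentage points if IST stops at month 3 and about 8-12 at month 6; for short tapers the effect is small.

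This rests on four assumptions: resumption means a restart after stopping; the 46% and its timing do not depend on taper speed; all patients stop in the same assumed month; and the curves describe timing adequately away from the quartiles.

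A reader might take this as a fault in the between-arm comparison or in the feasibility conclusion. It is neither: the randomization clock suits the comparison, and the primary endpoint counts enrolled patients. What is at risk is the interpretation of one descriptive rate and its use in planning the larger trial.

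**What to change.** Keep the free taper, and keep the endpoint at 12 months from randomization for comparing arms. Then:
- Add the actual IST stop date to the monthly contact in section 6.5.
- In section 7.1.2, for the comparison with the retrospective data only, report discontinuation-arm resumption timed from actual IST stop. Give the months off IST observed, censor at last follow-up, and use the annual chart review for restarts after month 12.
- Report the proportion of the arm off IST by month 12.
- Optionally, record the physician's planned off-IST date before allocation, if the provider survey does not already hold it.

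The cost is one item in the monthly contact and one descriptive table, plus one form field if the optional item is adopted. The downside is that a from-stop rate leaves out patients who never stop, so section 7.1.2 should say that it must not be used to compare arms.

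### Section 6.1 dose table: the under-18 alternate-day prednisone limit has no weight term and cannot be squared with the per-kg daily limit beside it

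*Combined protocol and SAP*

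**What the plan says.** Section 6.1 says that the dose to be continued in the continuation arm "will be determined by the attending physician at the time of enrollment based on the following overarching guidelines in the table below". Patients in that arm "will continue a fixed dose IST for an additional 9 months with no taper".

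The prednisone row of the table has one cell per age group, each with two alternatives joined by 'or':

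- Adults: less than 20 mg daily, or "< 40 mg every other day".
- Under 18: "< 0.25 mg/kg/day", or "< 0.5 mg every other day".

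The only other under-18 dose amount in the table is for mycophenolate mofetil: "Continuation dose ≤ 7.5 mg/kg BID". Cyclosporine, tacrolimus and sirolimus are limited by drug level, and any other agent is left to the treating physician. No other section restates or corrects the under-18 prednisone limits.

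**The concern.** Two limits offered as alternatives in one cell are in different units: one per kg of body weight, the other a flat amount in mg. They give very different ceilings for the same child, and the gap widens with weight. An alternate-day regimen whose average daily dose lies above 0.25 mg but below 0.25 mg per kg is over the alternate-day limit, yet would be under the daily limit if the same average were given daily.

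The dose chosen from this table has several uses in the trial:

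- It is held fixed for 9 months in the continuation arm.
- It determines when a patient is randomized, because those enrolled before reaching it are to be randomized before they get there (sections 6.1 and 6.5).
- It is the level from which a dose increase would be judged in the continuation arm (section 3.2).
- Adherence to arm-specific management of immunosuppression is a secondary measure (section 7.1.2).

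The practical stake is a clear dose limit for children on alternate-day prednisone. No planned analysis takes the cell itself as an input.

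**Working it through.** **Inputs, all from the section 6.1 table.** Adult limits: 20 mg/day and 40 mg every other day. Under-18 limits: 0.25 mg/kg/day and 0.5 mg every other day. For illustration I use weights of 10, 25 and 40 kg, taken from the edges of the paediatric blood-volume bands later in section 6.1. The documents give no enrolment weights.

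**Step 1: adult pair.** Two-day total under the daily limit: 20 × 2 = 40 mg. Printed alternate-day limit: 40 mg. Ratio 40/40 = 1, so the two adult options agree exactly.

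**Step 2: under-18 pair.** Two-day total under the daily limit: 0.25 × 2 = 0.5 mg per kg. Printed alternate-day limit: 0.5 mg in total. The numeral is the same but the unit is not. For weight *w* in kg, the ratio is (0.25 × *w* × 2) / 0.5 = *w*.

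| Weight | Daily limit | Two-day total, daily option | Two-day total, alternate-day option | Ratio |
|---|---|---|---|---|
| 1 kg | 0.25 mg/day | 0.5 mg | 0.5 mg | 1 |
| 10 kg | 2.5 mg/day | 5 mg | 0.5 mg | 10 |
| 25 kg | 6.25 mg/day | 12.5 mg | 0.5 mg | 25 |
| 40 kg | 10 mg/day | 20 mg | 0.5 mg | 40 |

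As an average, the alternate-day option is 0.5/2 = 0.25 mg/day at every weight.

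**Step 3: the rest of the table.** There are three paediatric dose amounts: mycophenolate, daily prednisone and alternate-day prednisone. The first two are per kg; only the third has no weight term.

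**Step 4: how many patients.** The documents give neither the share of children nor the share on alternate-day dosing. I assume 10–30% children. Section 6.2 reports prednisone as the last agent in 28% of the retrospective study; section 1 describes the retrospective series as adults, so this figure may not carry over to children.

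- Enrolled: 40 × 0.28 × 0.10 = 1.12 to 40 × 0.28 × 0.30 = 3.36.
- Continuation arm: 20 × 0.28 × 0.10 = 0.56 to 20 × 0.28 × 0.30 = 1.68.

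These are children on prednisone by any schedule. Those on alternate days are a subset, possibly none.

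**The case against.** The strongest case against giving this much weight runs as follows.

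- **The table is guidance.** Section 6.1 has the physician set the dose "based on the following overarching guidelines in the table below", section 6.2 deliberately accepts variation in the continued dose, and the row for other agents sets no number. This stands. It lowers the risk but does not make the guidance coherent.
- **The fold differences are only body weight restated.** This is correct: they measure a mismatch of units, not a difference in dose that any child is known to have received. They should be read that way.
- **A child on alternate-day dosing has exactly one printed limit.** Read literally, that is true. The contradiction is between the two schedules offered as alternatives, not within the alternate-day entry.
- **Equivalence of the schedules is inferred.** The documents never state it. The inference rests on the adult pair, which matches exactly, and on the per-kg form of the other paediatric amounts. It is a strong inference, but not a stated rule.
- **The head-count is soft and overcounts.** This also stands. It supports only the statement that few patients are involved.
- **The cell may be damaged by text extraction.** The adult column heading in this table gives the age without an inequality sign, so a symbol may have been lost there. Loss of the weight term is less likely, because the per-kg unit is plain text and survives both in the same cell and in the mycophenolate row. It still needs checking.

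None of these points reconciles the two entries.

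**Conclusion.** The concern holds. As printed, the two under-18 prednisone limits agree only at 1 kg and differ by a factor equal to body weight in kg, which is 10 to 40 at the illustrative weights. The arithmetic is exact. That the entries were meant to correspond is an inference from the rest of the table, and the finding assumes that the cell was extracted correctly.

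The reach is narrow: children on alternate-day prednisone, probably no more than one or two in the continuation arm under the assumed shares, and possibly none. The primary endpoint (number enrolled in 2 years), the sample size of 40 and the power statement are unaffected. It should nevertheless be fixed, because it is a contradictory dose limit for children in the table that guides a treatment held constant for 9 months. Confidence is moderate until the source PDF is checked.

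**What to change.** First compare the cell, and the age headings of the table, with the sponsor's source PDF. If the cell reads as shown, the sponsor should reconcile the two under-18 prednisone entries so that they are in consistent units and their relation to each other is clear. If a difference between the schedules is intended, the protocol should say so and give the reason. Which value is right is for the sponsor's clinical team to decide.

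The cost is one table cell in an amendment. No change to the design, the sample size or the analysis is needed.
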